**From visual acuity:**

- Mean change in best corrected visual acuity (BCVA) from Baseline to visits up to Day 180.
- Mean change in BCVA from Day 90 to Day 180.
- Proportions of patients gaining  $\geq 5$ ,  $\geq 10$  and  $\geq 15$  ETDRS letters from Baseline at visits up to Day 180.
- Proportion maintaining vision ( $< 15$  ETDRS letters lost from baseline) at visits up to Day 180.

The analysis of the secondary efficacy objectives will focus on the FAS. At all time-points assessed, each efficacy variable will be presented graphically and descriptive statistics provided based on absolute values and changes from baseline.

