Data will be analyzed by [REDACTED] according to the data analysis section 9 of the study protocol which is available in Appendix 16.1.1 of the clinical study report (CSR). Important information is given in the following sections and details are provided, as applicable, in Appendix 16.1.9 of the CSR.

Following are the changes from the protocol planned analysis:

- [REDACTED]
- SF volume and IRC volume were mentioned in the protocol as secondary efficacy variables. Due to technical limitations, there is no robust way in the reading center to assess these two parameters. CSRT thickness and subfoveal retinal thickness will be used to assess SF volume, and maximum height of intra-retinal cysts (IRC) will be used to assess IRC volume.
- ‘Intra-retinal cystoid changes’ was listed as a variable in the secondary objectives section. This is being assessed by presence of intraretinal fluid and whether some of the intraretinal fluid is of cystoid origin.
- [REDACTED]

This is a phase IV, unmasked, uncontrolled, single arm, and multicenter study in patients diagnosed with visual impairment due to nAMD who have been treated with aflibercept and where either no treatment response has been achieved or where there is suboptimal treatment response. The study will enroll 150 patients in 30 ophthalmology centers in Western European countries. Patients will be enrolled according to 2 subgroups: primary treatment failure subgroup (maximum of 30 patients) or suboptimal response subgroup.

The study includes 8 study visits over a minimum of 6 months. All patients with nAMD and eligible to enter the study will receive 3 monthly intravitreal (IVT) ranibizumab 0.5mg injections followed thereafter by monthly IVT injections of ranibizumab 0.5mg on a pro re nata/administer as required (PRN) basis. There will be 3 periods in this study: Screening period from Day -70 to Day 0, Monthly Treatment period from Baseline (Day 1) to Day 60, and PRN Treatment period from Day 61 to Day 180.

All assessments will be performed according to the assessment schedule (see Table 6-1 and Table 6-2 in Section 6 of the protocol).

The purpose of this study is to determine, in patients with nAMD treated with aflibercept and where there is evidence of persistent or increasing disease activity, whether switching treatment to ranibizumab 0.5mg reduces disease activity over a 6 month period as assessed by a variety of measures.

2 Statistical and analytical plans

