2.2.2 Secondary objectives

2.2.2.1 Variables

Secondary variables are:

From OCT

- Change from baseline to visits up to Day 180 in
 - Subfoveal Retinal Thickness (SRT) (*GRADE*: SUBFOVTK),
 - Central Subfield Retinal Thickness (CSRT) (*GRADE*: CSTTHK),
 - Central Subfield Retinal Volume (CSRV) (*GRADE*: CSRVVOL).
- Presence or absence of qualitative OCT parameters:
 - Intraretinal fluid (*GRADE*: RETFL),
 - Intraretinal fluid of cystoid origin (*GRADE*: RETIRC)
 - Subretinal fluid (SF) (*GRADE*: RETFLSF)
 - Intraretinal/subretinal fluid within the central subfield (diameter 1000 microns) (*GRADE*: RETSF)
 - Pigment epithelial detachments (PEDs) (*GRADE*: PEDDET),

- Dry retina. Dry retina is defined as eye without intraretinal fluid (RETFL from derived.grade) AND eye without subretinal fluid (RETFLSF from derived.grade) AND eye without intraretinal cysts (RETIRC from derived.grade)
- Change from baseline to visits up to Day 180 in PED height (*GRADE*: PEDHEIGHT) and diameter (*GRADE*: PEDDIAM) and IRC height (*GRADE*: IRCHEIGHT).
- Frequency of qualitative change OCT parameters:
 - Change from previous visit, each visit up to Day 180 in intraretinal fluid (*GRADE*: INTRAFL)
 - Change from previous visit, each visit up to Day 180 in subretinal fluid (SF) (*GRADE*: SUBRETFL)
 - Change from previous visit, each visit up to Day 180 in intraretinal/subretinal fluid within the central subfield (*GRADE*: SUBCENT)
 - Change from previous visit, each visit up to Day 180 in the pigment epithelium detachment (PED). (*GRADE*: CHAGPED)

or **From visual acuity (for study eye and fellow eye)**

- Change in BCVA from baseline to visits up to Day 180.
- Change in BCVA from Day 90 to Day 180.
- Proportions of patients with change from baseline in ETDRS letters for the following categories ≤ -15 , > -15 to < 0 , ≤ 0 to < 5 , ≥ 5 to < 10 , ≥ 10 to < 15 and ≥ 15 ETDRS letters from baseline at visits up to Day 180.

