2.2.2.2 Descriptive analyses

The analysis of the secondary efficacy objectives will be performed on the FAS.

No replacement of missing data will be done.

[figure not shown]
Data from visual acuity will be summarized for study eye and fellow eye separately.

[figure not shown]
Continuous secondary variables will be summarized presenting the absolute values and changes from baseline by visit, and will also be plotted over time.

[figure not shown]
Waterfall plot for change in number of letters for BCVA will be presented.

[figure not shown]
Qualitative secondary variables will be summarized presenting the number and percentage of patients for each modality by visit, and will also be presented graphically over time using bar charts.

All secondary variables details, including derived variables, will be listed.

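### The third BCVA change category in the SAP is wrong as written: ≤ 0 to < 5 overlaps both loss categories and leaves gains of 1 to 4 letters unclassified

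*SAP*

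**What the plan says.** Under visual acuity, SAP 2.2.2.1 (Variables) lists "Proportions of patients with change from baseline in ETDRS letters for the following categories", at visits up to Day 180, for the study eye and the fellow eye. The six bands are:

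1. ≤ -15
2. > -15 to < 0
3. ≤ 0 to < 5
4. ≥ 5 to < 10
5. ≥ 10 to < 15
6. ≥ 15

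SAP 2.2.2.2 states how the bands become output: "Qualitative secondary variables will be summarized presenting the number and percentage of patients for each modality by visit", with bar charts over time. It also states that missing data are not replaced and that "The analysis of the secondary efficacy objectives will be performed on the FAS". SAP 2.5 carries all the summary tables and listings of Section 2.2.2 into the interim analysis, whose results are to be submitted for publication.

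Protocol 9.5.1, under visual acuity, frames the same information cumulatively. It has "Proportions of patients gaining" at least 5, 10 and 15 letters, and "Proportion maintaining vision", defined as fewer than 15 letters lost from baseline.

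**The concern.** Bands 2, 4 and 5 each give a lower limit and then an upper limit. Read in the same way, the lower limit of band 3 is not a lower limit at all: a change that is both ≤ 0 and < 5 is simply a change ≤ 0. Band 3 then contains all of bands 1 and 2, and nothing covers +1 to +4.

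What is at stake is a table and bar chart produced at every visit, for both eyes, in the interim and the final reports. If it is programmed as printed, eyes that lost letters are counted twice, eyes with a small gain disappear, and the band meant to show stable or slightly improved vision mostly shows losses. If the programmer silently corrects the sign, the output is right but does not follow the written specification.

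**Working it through.** **Inputs.** The six band limits come from SAP 2.2.2.1 and the protocol endpoints from Protocol 9.5.1. The plan states no figure that can be reproduced here, and no sample size, power or alpha is involved.

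**Step 1: enumerate.** Every whole-letter change x from -100 to +100 (201 values) was placed in the six bands under three readings of band 3.

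| Reading of band 3 | Values in no band | Values in two bands |
|---|---|---|
| Literal: x ≤ 0 and x < 5 | +1, +2, +3, +4 | all 100 losses, -100 to -1 |
| Loose: anything below 5 | none | all 100 losses, -100 to -1 |
| 0 ≤ x < 5 | none | none |

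Only the third reading puts each value in exactly one band.

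**Step 2: size of the misclassification, literal reading.** The documents give neither a mean nor an SD for BCVA change, so both are assumed: normal, mean 0, SD s of 5 or 8 letters, rounded to whole letters. Φ is the standard normal distribution function.

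- Unclassified: P(+1 to +4) = Φ(4.5/s) - Φ(0.5/s).
  - s = 5: Φ(0.9) - Φ(0.1) = 0.816 - 0.540 = 0.276.
  - s = 8: Φ(0.5625) - Φ(0.0625) = 0.713 - 0.525 = 0.188.
- Counted twice: P(loss) = Φ(-0.5/s).
  - s = 5: Φ(-0.1) = 0.460.
  - s = 8: Φ(-0.0625) = 0.475.
- Total of the six percentages: 100 + counted twice - unclassified.
  - s = 5: 100 + 46.0 - 27.6 = 118.4%.
  - s = 8: 100 + 47.5 - 18.8 = 128.7%.

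The share in band 3 itself would be Φ(0.5/s), which is 54.0% (s = 5) or 52.5% (s = 8). The intended 0 to 4 letter band would hold Φ(4.5/s) - Φ(-0.5/s), which is 81.6 - 46.0 = 35.6% or 71.3 - 47.5 = 23.8%.

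**Step 3: can the protocol's endpoints still be obtained?** Under all three readings:

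- fewer than 15 letters lost (x > -15) = 100% minus band 1;
- gain ≥ 5 = bands 4 + 5 + 6;
- gain ≥ 10 = bands 5 + 6;
- gain ≥ 15 = band 6.

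None of these uses band 3. The denominator is patients with a non-missing change at that visit, since SAP 2.2.2.2 replaces no missing values. Maintained vision obtained by adding bands 2 to 6 is correct only once band 3 is corrected.

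**The case against.** The strongest reply is that this is a plain one-character slip. Band 2 ends below 0 and band 4 starts at 5, so only 0 to below 5 fits between them, and percentages totalling well over 100 would be noticed at once. The intent is indeed clear, and a careful programmer would probably recover it. That limits the likely harm. It does not make the written rule correct, and a pre-specified category should not rest on a guess.

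A second reply is that the sign may have been misread when the PDF text was extracted. This cannot be excluded and should be checked against the signed SAP. The other signs in the list form a consistent sequence, which makes a fault confined to this one sign less likely.

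The documents do not support two stronger readings that a reader might infer:

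- **That the protocol's maintained-vision and responder endpoints are no longer produced.** The SAP does not list maintained vision, or the cumulative ≥ 5 and ≥ 10 gains, by name. But the number and percentage in each band are reported by visit, and every one of these proportions follows exactly by complement or summation from bands that the error does not touch. What remains is a matter of presentation.
- **That the SAP changed these endpoints without declaring it.** The SAP opens with a list introduced by "Following are the changes from the protocol planned analysis". No visible item concerns BCVA categories, but two of the four items are blacked out, so nothing can be concluded from the visible ones.

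**Conclusion.** Wrong as written, with minor impact. The printed third band overlaps both loss bands and, read literally, omits gains of 1 to 4 letters. That conclusion follows from the band limits alone and needs no distributional assumption; it assumes only that the printed sign is the one in the signed SAP.

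The size does rest on an assumption. With a normal change of mean 0 and SD 5 to 8 letters, roughly 28% to 19% of eyes would be unclassified and 46% to 48% counted twice, with percentages totalling about 118% to 129%. A different mean or SD would move these figures.

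The error is confined to the categorical BCVA tables and bar charts, interim and final. The mean BCVA changes and the BCVA waterfall plot use the letter change itself and are unaffected, as is the primary CSRT analysis.

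**What to change.** In SAP 2.2.2.1, change the third category to ≥ 0 to < 5, and carry the same limits into the table shells and programs for the interim and final analyses. The cost is one symbol, and no new data are needed.

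Optionally, add four derived rows by visit for the study eye: gain ≥ 5, gain ≥ 10, gain ≥ 15, and fewer than 15 letters lost (change > -15). State the denominator as patients with a non-missing BCVA change at that visit. A 95% CI could accompany each row, since SAP Section 2 already allows one for categorical summaries where appropriate. Alternatively, one sentence saying that the protocol's cumulative endpoints are obtained from the bands by summation or complement would serve the same purpose.

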2.2.2.2 Descriptive analyses

The analysis of the secondary efficacy objectives will be performed on the FAS.

No replacement of missing data will be done.

[figure not shown]
Data from visual acuity will be summarized for study eye and fellow eye separately.

[figure not shown]
Continuous secondary variables will be summarized presenting the absolute values and changes from baseline by visit, and will also be plotted over time.

[figure not shown]
Waterfall plot for change in number of letters for BCVA will be presented.

[figure not shown]
Qualitative secondary variables will be summarized presenting the number and percentage of patients for each modality by visit, and will also be presented graphically over time using bar charts.

All secondary variables details, including derived variables, will be listed.

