## **1.2 Purpose**

The purpose of this study is to determine, in patients with nAMD treated with aflibercept and where there is evidence of persistent or increasing disease activity, whether switching treatment to ranibizumab 0.5mg reduces disease activity over a 6 month period as assessed by a variety of measures.

[figure not shown]

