## **4 Population**

The study will include patients diagnosed with visual impairment due to nAMD who have been treated with aflibercept and where either no treatment response has been achieved or where there is suboptimal treatment response. Assuming an approximate 20% screen failure rate, approximately 155 patients will need to be screened to have 124 eligible patients commencing treatment in the trial. Approximately 40 ophthalmology centers in Western European countries will be initiated.

It is anticipated that patients with primary treatment failure to aflibercept (see Section 4.1 for definition) are likely to achieve small responses to treatment with ranibizumab. In order to minimize potential risks to these patients, a maximum of 30 patients will be recruited in this subgroup.

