**Table 5-1 Prohibited treatment**

Medication	Action to be taken
Anti-VEGF drugs other than ranibizumab (ocular or systemic)	Withdraw patient from study
Intra- or periocular corticosteroids (including sub-tenon but excluding topical formulations) – study eye only	Withdraw patient from study
Intra-ocular corticosteroid implants – study eye only	Withdraw patient from study
Investigational drugs and interventions of any type	Withdraw patient from study

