### 5.5.9 Discontinuation of study treatment

Patients may voluntarily discontinue study treatment for any reason at any time.

The study and treatment completion dates will be determined by the last visit the patient came to the clinic.

The Investigator must provide follow-up medical care for all patients who are prematurely withdrawn from the study, or must refer them for appropriate ongoing care. Patients who are prematurely withdrawn from the study will not be replaced by an equal number of newly enrolled patients.

Patients can discontinue study treatment because of the appearance of a new health condition suspected to require appropriate care or require medications prohibited by the protocol (Section 5.5.8), unacceptable AEs, refusal to continue treatment, or at the Investigator's discretion based on his or her clinical judgment.

The Investigator should discontinue study treatment for a given patient or withdraw the patient from study if, on balance, he/she believes that continuation would be detrimental to the patient's well-being.

Study treatment must be discontinued under the following circumstances:

- Withdrawal of informed consent
- Emergence of the following AEs:
  - Stage 3 or 4 macular hole
  - Stroke or transient ischemic attack
  - Rhegmatogenous retinal detachment
- Pregnancy
- Use of prohibited treatment in Table 5-1
- Two sequential ranibizumab injections to the study eye should have occurred according to the protocol specified monthly/PRN treatment period criteria but were withheld (see Section 5.5.5) or missed.

- Any other protocol deviation that results in a significant risk to the patient's safety.

Patients who permanently discontinue study treatment and start a prohibited non-study treatment (see Section 5.5.8) should be withdrawn from the study and undergo all assessments for End of Study visit as described in Table 6-1 and Table 6-2.

Patients who discontinue study treatment but do not receive prohibited treatment should not be considered withdrawn from the study and may continue their scheduled follow-up assessments until End of Study.

The Completion/Withdrawal eCRF page should be completed, providing the primary reason for stopping study treatment.

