### **9.4.3 Handling of missing values/censoring/discontinuations**

In the event that CSRT is missing for Day 90, the analysis will follow an LOCF (Last Observation Carried Forward) approach for the Full Analysis Set. This will only be done for the primary outcome.

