2.2.1.2 Descriptive analyses

The change in CSRT from baseline to Day 90 will be summarized together with the 95% CI for the mean and absolute values of CSRT at baseline and at Day 90.

In the event that CSRT is missing for Day 90, the analysis will follow an LOCF (Last Observation Carried Forward) approach for the FAS.

The primary analysis will be performed on the FAS.

For sensitivity purposes, the primary analysis will be repeated using the PPS.

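### Secondary results after Day 90 use observed values only and are open to outcome-related dropout; the SAP does not say whether early-withdrawal values count as Day 180

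*SAP*

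**What the plan says.** The stated aim is to learn "whether switching treatment to ranibizumab 0.5mg reduces disease activity over a 6 month period" (Protocol 1.2). The primary variable stops at Day 90, so the evidence for months 4 to 6 lies in the secondary variables.

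- **Secondary analysis.** SAP 2.2.2.2: "The analysis of the secondary efficacy objectives will be performed on the FAS", and "No replacement of missing data will be done". Continuous variables are summarised by visit and plotted over time.
- **Primary analysis.** SAP 2.2.1.2: "In the event that CSRT is missing for Day 90, the analysis will follow an LOCF (Last Observation Carried Forward) approach for the FAS". Protocol 9.4.3 adds: "This will only be done for the primary outcome". The Day 90 LOCF rule is not at issue here.
- **Withdrawal.** Protocol Table 5-1 lists "Anti-VEGF drugs other than ranibizumab (ocular or systemic"), with withdrawal from the study as the action. Protocol 5.5.9 agrees: "Patients who permanently discontinue study treatment and start a prohibited non-study treatment (see Section 5.5.8) should be withdrawn from the study". The same sentence goes on to require the full set of End of Study assessments for these patients.
- **Visit label.** Table 6-1 places the early withdrawal visit in the V8 column together with Day 180. OCT and BCVA are both marked there.
- **Stopping without another drug.** Under Protocol 5.5.9, patients who stop ranibizumab but take no prohibited treatment are not withdrawn and may continue their visits.

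**The concern.** A patient whose disease stays active and who moves to another anti-VEGF drug leaves the study and has no later scheduled visits. The Day 120 and Day 150 means then describe the patients who remained, and those may be the better responders. Section 4 of the protocol expects that primary treatment failures, up to 30 of 124 (24%), "are likely to achieve small responses to treatment with ranibizumab". The group from which such exits might come is therefore not small.

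The effect could be a curve that shows sustained or growing benefit after Day 90 because its denominator has changed. There is no control arm against which to see this. The visible text plans no model and no missing-data sensitivity analysis for the secondary variables, and the PPS repeat covers only the primary analysis.

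Day 180 has a second problem. Withdrawn patients do have an exit OCT and BCVA, filed under V8. The visible SAP does not say whether these values are tabulated as Day 180, moved to the visit nearest their date, or left out.

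**Working it through.** **1. Inputs.** The documents give no withdrawal rate and no outcome for patients who leave. The SD of CSRT change, 102 µm, is known from the summary of Amendment 2; section 9.7 is not in the available text. That summary is consistent with itself: 162 × (102/117)² = 123.1, against the stated 124. With two-sided 5% and no dropout allowance, 124 patients correspond to

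- 90% power: (1.96 + 1.282) × 102/√124 = 29.7 µm
- 80% power: (1.96 + 0.842) × 102/√124 = 25.7 µm

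Other combinations fit 124 equally well (for example 25 µm, 80% power, one-sided, 15% dropout). The -30 µm used below is thus an assumption about scale and not the plan's stated effect.

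**2. Simple bound.** Let d be the share missing at a visit and g the amount by which the mean reduction is smaller in missing than in observed patients. The observed-case mean overstates the reduction by d × g.

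- CSRT, d = 5% to 20%, g = 30 to 60 µm: 0.05 × 30 = 1.5 µm up to 0.20 × 60 = 12 µm.
- BCVA, g = 5 to 10 letters: 0.05 × 5 = 0.25 up to 0.20 × 10 = 2.0 letters.
- If g = 0 there is no bias. If missing patients did better, the sign reverses.

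For scale, the 95% CI half-width for mean CSRT change is 18.6 µm at n = 118 (5% missing) and 20.3 µm at n = 99 (20% missing).

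**3. Simulation by visit.** Assumptions: 124 patients; normally distributed change with SD 102 µm; true means -20, -27 and then -30 µm from Day 90 on; equal between-visit correlation of 0.7; and, at Days 90, 120 and 150, a 10% chance of leaving if the current CSRT is above Baseline. Total withdrawal is about 10.7%.

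| Visit | True mean | Observed mean, exit values left out | Mean with exit values counted as Day 180 |
|---|---|---|---|
| Day 120 | -30 | about -33 | not affected |
| Day 150 | -30 | about -36 | not affected |
| Day 180 | -30 | about -38 | -27 or -30 |

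In the last cell, -27 applies if the exit value equals the reading that triggered withdrawal, and -30 if it is a fresh reading one visit later.

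**4. Cross-check of steps 2 and 3.** With d = 0.107 and an observed Day 180 mean of -38.3, the leavers' mean is (-30 + 0.893 × 38.3)/0.107 = 4.2/0.107 ≈ +39 µm. So g ≈ 38.3 + 39 = 77 µm, and 0.107 × 77 ≈ 8.3 µm = 38.3 - 30. This scenario is harsher than the 30 to 60 µm in step 2.

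**5. Range.** Vary the correlation from 0.5 to 0.8 and the exit chance from 3% to 15% per visit, giving total withdrawal of about 3.5% to 16%. The Day 180 reduction is then overstated by 6% to 48% if exit values are left out. If they are counted as Day 180, the mean is -21.7 to -30.2 µm: unbiased or understated.

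**6. Likelihood-based estimate.** In the step 3 scenario, a repeated-measures estimate gives about -30 µm. That agreement is built in, because simulated exit depends only on values already observed.

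**The case against.** A reader might infer that the plan analyses only patients still in the study and that the 6-month benefit is therefore overstated. The documents do not support this.

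- Patients withdrawn for another anti-VEGF have an exit OCT and BCVA, labelled V8 like Day 180. If V8 is read as Day 180, the bias there disappears or reverses.
- Failure to respond does not itself lead to withdrawal. Patients who stop ranibizumab without prohibited treatment may stay in follow-up.
- No withdrawal rate is given. The exit chances above are assumed, and every simulated exit follows thickening; other reasons for leaving are ignored.

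There is more on the plan's side. The secondary analyses are descriptive in the visible text, so no error rate is at stake. Protocol 3.2 calls the study exploratory and accepts some bias. The SAP reports the number of non-missing values, tabulates withdrawals with primary reasons, and lists all data. In the worked scenario the bias of about 8 µm is well inside the CI half-width of roughly 19 µm. A mixed model has its own limit: it estimates outcomes as if leavers had continued like similar patients who stayed. Parts of the SAP's list of changes are redacted.

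These points rule out a firm direction at Day 180 and any firm size. They do not remove the concern. Days 120 and 150 remain observed-case however V8 is labelled, and under this mechanism the error leans one way. The withdrawal table is not by visit and corrects neither the means nor the plots. The silence on V8 also leaves two possible Day 180 results about 8 to 12 µm apart in the worked scenario.

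**Conclusion.** The concern holds in a limited form. Secondary results after Day 90 may be biased by outcome-related dropout, most clearly at Days 120 and 150, where the benefit may be overstated. In the worked scenario that is about 3 and 6 µm on a true 30 µm. At Day 180 the same scenario gives anything from about 8 µm overstatement to about 3 µm understatement, depending on a V8 rule that the visible SAP does not state. All sizes rest on assumed withdrawal rates, an assumed mean of -30 µm and assumed correlations; only the SD comes from the documents. For BCVA only the simple bound of 0.25 to 2.0 letters is available. The primary Day 90 analysis is not affected. The change should be made because the secondary results are the only evidence for the second half of the stated 6-month purpose.

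**What to change.** In SAP 2.2.2.2:

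1. Estimate by-visit mean change (95% CI) for the continuous secondary variables in the study eye, and the Day 90 to Day 180 BCVA change, from a mixed model for repeated measures on all FAS visits. Include visit, baseline value, subgroup and baseline-by-visit, with unstructured covariance. Report estimates for the whole FAS and use them for the plots.
2. Assign early-withdrawal V8 assessments to the scheduled visit nearest their actual date, not automatically to Day 180.
3. Keep the observed-case table as supportive, with the number missing and the reason at each visit.
4. Add one Day 180 sensitivity analysis that counts withdrawal for another anti-VEGF as no change from baseline. This is not a worst case: in the worked scenario it gives 0.893 × (-38.3) = -34.2 µm, because the simulated leavers are thicker than at Baseline.

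The cost is SAP wording and a modest amount of extra analysis, with no new data. The main model relies on values being missing at random given earlier visits, a weaker assumption than observed-case means need; item 4 tests it.
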